15.5 Enrollment/Stratification/Randomization/Blinding Procedures

This study uses a "precision" clinical trial framework that leverages prior information to target treatment adherence support to individuals based upon their characteristics (i.e., propensity for nonadherence) while preserving ability to assess the average treatment effect and differences by arms within groups defined by these characteristics (**Figure 15.5**). Specifically, an individual,

unblinded, unbalanced, blocked allocation approach based on prior information of the patient's propensity for failure will be used.

Data on early ART refills/HIV viral suppression (3-6 months after ART initiation) from existing ICCs will be used to develop an algorithm to predict propensity for HCV treatment failure. We are currently unaware of any large databases that contain information on SVR among active PWID in India that we could use and therefore, opted to use early ART refills/viral suppression among HIV-positive persons as a surrogate. The time frame being used is comparable to a full course of HCV treatment. We will develop the score using an approach that incorporates an internal-external cross validation

procedure⁹⁶ where the unit for splitting data will be study site. Each site will be left out once with validation conducted on the remaining pooled set of data. The final model is based on the pooled dataset which can be considered to be an externally validated model. This assures that the final model is based on the pooled data thus maximizing sample size while at the same time tempering overoptimistic model performance in an independent set of data.

In a preliminary analysis, among 119 clients newly initiating ART, we developed a model that had high predictive accuracy (area under the receiver operating characteristics curve=0.81) for early adherence. Importantly all of the factors included in this model (age, employment, injection frequency, OAT use, living with spouse/family, having told someone about their HIV status and readiness for treatment) are either routinely captured in the ICC or can be added to a brief intake survey. We will modify this algorithm based on an expanded analysis that includes ~500 persons initiating ART. We anticipate splitting at the median of the score but this will be reassessed once the model is complete. Distributions of the score within independent samples of the population will be assessed prior to implementation.

At the Entry visit, prior to randomization and treatment initiation, each participant will undergo a short survey to capture information on barriers/facilitators to treatment adherence identified in the prediction model. Responses to this survey will be captured in an eCRF and integrated with other data from the EHR. The algorithm will be used to classify persons into two strata according to their propensity for HCV treatment failure (minimal or elevated risk).

Individuals will be preferentially randomized to the support level that matches their failure risk. Those at elevated risk for treatment failure will be randomized at an allocation ratio of 3:2:1 for high, medium and low intensity support respectively. Those at minimal risk will be randomized at a ratio of 1:2:3 to high, medium and low-intensity support, respectively.

Randomization will be integrated into the EHR. The Study Nurse who will complete the survey will receive the determination of study arm from an automated program. Both study staff and study participants will be blinded to the designation of minimal/elevated risk stratum.

15.6 Participant Enrollment and Follow-up

We anticipate enrolling 3,000 (approximately 420 per site) persons over a period of 18-24 months with an average of 15-20 participants per site per month. After enrollment, participants will be followed while they are on treatment (for 12 or 24 weeks) through to an SVR evaluation visit 10 – 60 weeks after treatment completion. This will be the minimum amount of follow-up for all those enrolled. Following this, those who achieve SVR and those who are HIV/HCV co-infected (regardless of SVR) will have semi-annual visits thereafter to monitor reinfection. Follow-up will be complete at the SVR evaluation visit for those who do not achieve SVR and are not HIV/HCV coinfected. The maximum follow-up post the SVR evaluation visit for those who achieve SVR is 30 months for a total follow-up of 36 months. The goal will be that everyone who achieves SVR has at least one semi-annual visit after the SVR evaluation visit but it is possible that some individuals who are enrolled late do not have any post SVR follow-up.

15.7 Data and Safety Monitoring

Data from the trial will be reviewed monthly with more formal Data, Safety, and Monitoring (DSM) reports occurring approximately semi-annually from first participants' first visit date. In addition, a Data and Safety Monitoring Board (DSMB) will be formed that includes four to five members with relevant expertise (e.g., PWID, HCV treatment, treatment interventions, biostatistics/clinical trial design and monitoring) but who are independent from the study investigators with no conflicts of interest. See details in the **Data and Safety Monitoring Plan**.

15.7.1. Planned interim analyses and stopping guidelines

No interim analysis will be conducted as power to detect differences will be limited for the stratum specific analyses which represent the primary outcome.

15.7.2. Analysis plan

A brief description of primary and secondary outcome analyses is provided below. Additional details particularly on sensitivity analyses, exploratory analyses and subgroup analyses can be found in the Statistical Analyses Plan

15.7.2.1. Primary outcome.

The primary individual-level outcome is sustained virologic response (SVR) defined as HCV RNA < lower limit of quantification (LLOQ) 10 – 60 weeks after completion of treatment (cure). The primary analysis will be intention to treat and will be stratified by the risk of treatment failure (minimal and elevated).

The primary analysis will compare the proportion achieving SVR across level of support (low, medium, high intensity) within the two strata of risk (minimal and elevated) independently. Using a log-binomial or poisson regression model (due to the high prevalence of the outcome) with adjustment for site, in the elevated risk stratum, the proportion achieving SVR in those who received the low or moderate intensity interventions will be compared to those who received the high intensity intervention (in separate models) resulting in a relative risk (RR).

Primary comparisons will be intention to treat. That is the study population for this analysis will include everyone who was randomized. Individuals with missing data on the outcome of interest either due to loss-to-follow-up or death will be treated as failures. For those at minimal risk of failure, analyses will be similar.

Per protocol analysis. We will conduct a per protocol analysis which will exclude individuals which will exclude individuals who died prior to SVR assessment, who are alive but lost to follow-up (i.e., do not complete the SVR visit) and those who prematurely discontinued treatment. The study population for this analysis will include everyone who was randomized, completed a treatment course and completed the SVR evaluation visit.

Sensitivity Analyses. The Statistical Analysis protocol describes several sensitivity analyses to account for study site differently and to account for covariates that are differentially distributed by arm or are prognostic for the outcome. Additionally, we will conduct additional analyses of the primary outcome to account for missing data/nonadherence related to the primary outcome. Of interest is estimating the most beneficial effect of the higher intensity intervention as if everyone fully complied and there were no losses to follow-up or nonadherence to the intervention. Therefore, missing data will result from persons who do not complete the SVR visit within the window including both those who are lost to follow-up before and after treatment completion. We will conduct an additional per protocol analysis which will exclude individuals who are alive but lost to follow-up (i.e., do not complete the SVR visit) but account for the informative lost to followup using inverse probability censoring weights. Further, we will include the randomization to the different intervention arms as an instrumental variable. An instrumental variable analysis estimates the "complier" average treatment effect. Therefore, by using the randomization as an instrumental variable for the treatment arms, we would be able to estimate the complier treatment effect for those that fully comply with the intervention. A second approach will use fully specified conditional specification multiple imputation of the SVR outcome based on only two variables: treatment completion and adherence. In this analysis, undetermined SVR due to death will not be imputed; deaths will be treated as SVR failures. Additionally, assessing the relationship of the treatment arms with lost to follow-up is of interest in and of itself. This is because as an implementation strategy, policy makers would need to know the potential for loss to a program that they are implementing. Therefore, a time to lost to follow-up analysis will be examined using standard survival methods and accounting for prognostic score.

Non-inferiority analyses. Additionally, while the overall trial is designed to assess superiority, if there is a failure to identify that one support intervention is superior to another, sensitivity analyses will examine non-inferiority particularly within the minimal risk stratum using a prespecified non-inferiority margin (i.e., that among those at minimal risk for treatment failure, the low intensity intervention is non-inferior to the medium and high-intensity interventions).

Subgroup and Exploratory Analyses. These are described in the Statistical Analysis Plan.

15.7.2.2. Secondary outcomes.

Secondary outcomes are 1) treatment completion defined as completing the prescribed course of treatment (12/24 weeks); 2) self-reported adherence; 3) reinfection defined as testing positive for HCV Core Ag after achieving SVR; and 4) HIV viral suppression defined as HIV RNA<LLOQI.

Treatment completion (secondary outcome). Those who prematurely discontinue treatment or are lost-to-follow-up prior to the completion of this visit will be considered as failures for this analysis. Using a log-binomial or poisson regression model (due to the high prevalence of the outcome), with adjustment for site, in the elevated risk stratum, the proportion completing treatment in those who received the low or moderate intensity interventions will be compared to those who received the high intensity intervention (in separate models) resulting in a relative risk (RR). For those at minimal risk of failure, analyses will be similar.

Sensitivity analyses. Sensitivity analyses similar to the primary outcome are described in the Statistical Analysis Plan.

Non-inferiority analyses. As with the primary outcome, if there is a failure to identify that one support intervention is superior to another, sensitivity analyses will examine non-inferiority particularly within the minimal risk stratum using a pre-specified non-inferiority margin (i.e., that among those at minimal risk for treatment failure, the low intensity intervention is non-inferior to the medium and high-intensity interventions).

Subgroup analyses. These are described in the Statistical Analysis Plan.

Adherence (secondary outcome). Adherence will be defined both using both self-reported data and objective data on refills completed and pill counts. It will be analyzed as both a continuous outcome (e.g., percentage of doses reported as taken; percentage of doses taken according to refills completed/pill counts) and a dichotomous variable (e.g., >90% of doses reported as taken; >90% of doses taken according to refills completed/pill counts). We will use both self-reported adherence as well as For the dichotomous adherence outcome, analyses will be conducted as they are specified for the primary outcome. For the continuous variable, the analysis will compare the percentage value of adherence across level of support (low, medium, high intensity) within the two strata of risk. Using a linear regression model, in the elevated risk stratum, the difference in adherence level for those who received the low and moderate intensity interventions will be compared to those who received the high intensity intervention. In this analysis, adherence will be calculated based on the data from the surveys at 4, 8 and 12 weeks. The comparisons will be adjusted only for site. For those at minimal risk of failure, analyses will be similar.

Per protocol analysis. We will conduct a per protocol analysis which will exclude individuals who died or were lost to follow-up before the end of treatment or who discontinued treatment prematurely.

Sensitivity Analyses. We will conduct sensitivity analyses as outlined in the Statistical Analysis plan similar to those described for the primary outcome include those to account for missing data due to missed visits. Specifically, we will use fully specified conditional specification multiple imputation of the SVR outcome based on available adherence reports.

Reinfection (secondary outcome). Reinfection will be defined as testing positive for HCV Core Ag after achieving SVR. This may be at any of the post SVR follow-up visits. To evaluate factors independently associated with reinfection, all clients who achieve SVR and have at least one subsequent HCV Core Ag assessment will be included. Using survival analysis, factors associated with reinfection will be assessed. These including ongoing substance use, needle sharing, OAT, SSP use, HIV status and frequency of visits to the ICC. We will also evaluate whether the risk stratum or intervention had impact on reinfection outcomes as well as the reinfection rate over time elapsed since treatment completion. In order to account for missing data due to loss-to-follow-up, we will use inverse-weighting methods.^{97,98}

HIV viral suppression (secondary outcome). Annual assessments of HIV viral load among HIV/HCV coinfected participants in the 7 ICCs are expected as part of other ICC activities and standard of care at Indian government ART centers. All available viral load measurements for HIV/HCV co-infected PWID enrolled in the trial will be used. Viral suppression will be defined as HIV RNA <LLOQ. We will compare viral suppression across two groups defined by primary outcome status, which will be cured vs. not cured using logistic regression with generalized estimating equations (GEE) to account for repeated measures within individuals. All potentially confounding factors known to be associated with HCV cure and HIV viral suppression in this population including demographics, substance use, needle sharing, OAT, SSP use, social support and frequency of visits to the ICC will be accounted for. Analyses will be combined across all groups but we will include a covariate for the classification of risk of treatment failure (minimal or elevated). To evaluate whether the intensity of HCV treatment support also had any impact on HIV viral suppression outcomes, a covariate for the intensity of intervention received will also be included. In order to account for missing data due to loss-to-follow-up, we will use inverseweighting methods. 97,98 Additional sensitivity analyses will vary the threshold for HIV viral suppression to account for blips, considering cutoffs of <200 copies/ml, <500 copies/ml and <1000 copies/ml.

15.7.2.3. Exploratory analysis.

Exploratory outcomes. These are described in the Statistical Analysis Plan.

Effect of delays in treatment completion on SVR. Additional exploratory analyses will evaluate the impact of non-adherence and delays in completing treatment on SVR. Initial analyses will incorporate data from all three arms. Two variables will be calculated: 1) the percentage of doses completed (as described above); and 2) days to treatment completion. While the scheduled course of treatment will be 84 days for most, participants will be instructed to take all of the doses prescribed (even if doses are missed and the total time for treatment completion extends beyond 84 days. In separate models, log-binomial regression will be used to estimate the association between 1) estimated adherence; and 2) days to treatment completion and SVR. These analyses will be combined across risk strata and treatment arm but these variables will be included as covariates. Additional analysis will be conducted exclusively among participants assigned to Arm 3 (high intensity support) where adherence data will be objectively collected using biometric data.

Estimation of heterogeneity in treatment effect and estimation of average treatment effect.

Additional analyses will be completed to estimate heterogeneity in treatment effect and the average treatment effect for the primary (SVR) and secondary outcomes (treatment completion) defined above.

The average treatment effect will be determined in order to estimate the effect of the different support strategies in the overall population. Under the unbalanced randomization scenario that is planned, a prognostic score is intentionally created. This score lies between the causal pathway from the individual characteristics to the treatment assignment, thus introducing an "informed confounding", i.e., the causal relationship between treatment assignment and outcome is confounded by the prognostic score (i.e., individual's propensity for treatment failure). To estimate the unbiased, average treatment effect, given that there is information on how the prognostic score affects study arm allocation, the targeted randomization can be used to reweight the sample back to the initial sample as if the randomization allocation was equivalent to all levels of the prognostic score. That is, by using inverse probability of treatment weights, the relationship between the prognostic score and treatment assignment is removed to estimate the average treatment effect to provide answers about whether the high and moderate intensity interventions resulted in superior outcomes in the overall population (i.e., is high intensity support a superior intervention to standard of care in all PWID regardless of propensity for treatment failure?).

These analyses will seek to use information from the prognostic score and the observed data to identify the optimal threshold for assigning treatment support. That is, by assessing heterogeneity in treatment effect by level of prognostic score, we will potentially be able to identify a range of scores to assist in the decision of whether low, moderate, or high level of support would be most efficacious for individuals based upon the characteristics that determine their prognostic score. First, within the two strata defined by the prognostic score, there remains variability in the prognostic score. Therefore, we will evaluate the impact of the interaction between the prognostic score and the intensity of support received (low, medium and high intensity) on SVR and treatment completion rates in the full sample. The goal of this analysis will be to evaluate the heterogeneity of treatment effect within strata.

Of additional interest is identifying the heterogeneous treatment effect of the intensity of support received on SVR and secondary outcomes across the *entire distribution of* prognostic score (note that the prognostic score will be continuous). Therefore, by using the weighted (by inverse probability of treatment weights) study sample, the interaction between the prognostic score and intensity of support received on SVR and treatment completion rates can be examined across the entire study population. Specifically, a model will include the indicator variables for level of support, the main effect of the prognostic score, and the interaction term. The model will allow for non-linear relationship between prognostic score and outcomes and depict the estimated treatment effect graphically to determine the optimal cut-points of the prognostic score to assign low, medium and high intensity treatment support to maximize SVR.

Effect of heterogeneity of intervention effect by gender. It is of interest to examine whether the impact of the intervention varies by gender. We anticipate that power will be limited in these analyses since in many of the field sites, the number of women is negligible, consistent with the epidemiology of injection drug use in India. However, we will conduct stratified analyses to explore whether the effect of the level of treatment support varies by gender within strata of treatment nonadherence risk. We will also conduct the analyses of the average treatment effect stratified by gender.

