15.3 Study Objectives and Hypothesis/Hypotheses

15.3.1. Primary objective / hypotheses

Primary objective: To evaluate whether the intensity of treatment adherence support affects sustained virologic response rates in HCV mono- and HIV/HCV co-infected participants receiving DAAs in PWID-focused centers

Hypotheses:

- Among PWID at elevated risk for treatment failure, PWID receiving the high intensity intervention will have significantly higher SVR than those receiving either the medium or the low intensity interventions.
 - 1a. Among PWID at minimal risk for treatment failure, PWID receiving either the high or the medium intensity intervention will have significantly higher SVR than those receiving the low intensity interventions.

The formal null hypothesis is no difference in SVR and the alternate is a difference in SVR. The trial is designed for superiority assessment; however, if there is failure to detect a statistically significant difference between support strategies across any particular stratum, a lesser objective of interest is non-inferiority with a pre-specified non-inferiority margin.

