15.3.2. Secondary objectives / hypotheses

15.3.2.1. To evaluate whether the intensity of treatment adherence support affects HCV treatment completion rates.

Hypothesis: Among PWID at elevated risk for treatment failure, PWID receiving the high intensity intervention will have significantly higher treatment completion than those receiving either the medium or the low intensity interventions.

Hypothesis: Among PWID at minimal risk for treatment failure, PWID receiving either the high or the medium intensity intervention will have significantly higher treatment completion than those receiving the low intensity interventions.

15.3.2.2. To evaluate whether the intensity of treatment adherence support affects HCV treatment adherence.

Hypothesis: Among PWID at elevated risk for treatment failure, PWID receiving the high intensity intervention will have significantly higher adherence than those receiving either the medium or the low intensity interventions.

Hypothesis: Among PWID at minimal risk of treatment failure, PWID receiving either the high or the medium intensity intervention will have significantly higher adherence than those receiving the low intensity intervention.

15.3.2.3. To estimate the incidence and correlates of HCV reinfection among HCV mono- and HIV/HCV coinfected PWID who achieve HCV cure.

Hypothesis: HCV reinfection will be lower among clients who have higher attendance at OAT programs.

15.3.2.4. To evaluate the impact of HCV cure on HIV viral suppression among HIV/HCV coinfected PWID.

Hypothesis: Among HIV/HCV co-infected PWID, HIV viral suppression will be higher after achievement of HCV cure.

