Annual assessments of HIV viral load among HIV/HCV coinfected participants in the 7 ICCs are expected as part of other ICC activities and standard of care at Indian government ART centers. All available viral load measurements for HIV/HCV co-infected PWID enrolled in the trial will be used. Viral suppression will be defined as HIV RNA less than LLOQ. We will compare viral suppression across two groups defined by primary outcome status, which will be cured vs. not cured using logistic regression with generalized estimating equations (GEE) to account for repeated measures within individuals. Because these groups will be defined by the primary outcome and no longer balanced by randomization, analysis will be adjusted for confounding factors including demographics, substance use, needle sharing, MOUD, SSP use, social support and frequency of visits to the ICC. Analyses will be combined across all groups but we will include a covariate for the classification of risk of treatment failure (minimal or elevated) and intervention received. In order to account for missing data due to loss-to-follow-up, we will use inverse-weighting methods.^{4,5}

2d.1. Sensitivity analyses. We will vary the threshold for HIV viral suppression (<150 copies/ml vs. 400 copies/ml vs. 1000 copies/ml) and will also incorporate the revised definition of SVR vs. treatment failure using sequence data.

3. Exploratory analysis

3a. Impact of interventions on medication for opioid use disorder (MOUD) utilization. Daily MOUD utilization data is available in the electronic health record. We will explore the impact of the interventions within strata by arm on new MOUD initiation and MOUD retention using methods of survival analysis, logistic regression with GEE and growth mixture models. Analyses will be adjusted for site. Additional sensitivity analyses will be similar to those reported in the primary and secondary outcome analyses and will include accounting for the prognostic score.

3b. Impact of interventions on quality of life.

Quality of life data is captured at the SVR visit and at semi-annual post-treatment follow-up visits. Using logistic and linear regression with GEE, we will explore the impact of interventions within strata on quality of life after treatment.

3c. Impact of interventions on mortality.

Using Poisson regression, we will explore the impact of interventions within strata on all-cause mortality.

3d. Effect of delays in treatment completion on SVR.

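### The protocol judges the impact of support intensity on HIV suppression from an arm coefficient in a model that also conditions on HCV cure, so it does not estimate the total effect of support

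*Protocol*

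**What the plan says.** Protocol 15.7.2.2 plans one logistic GEE for HIV suppression in co-infected participants. Its main contrast is cure: "We will compare viral suppression across two groups defined by primary outcome status, which will be cured vs. not cured using logistic regression". The covariates are "demographics, substance use, needle sharing, OAT, SSP use, social support and frequency of visits to the ICC will be accounted for", plus risk stratum. Arm is then added for a question of its own, whether support intensity "also had any impact on HIV viral suppression outcomes, a covariate for the intensity of intervention received will also be included".

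SAP 2d keeps this model. It adjusts for "demographics, substance use, needle sharing, MOUD, SSP use, social support and frequency of visits to the ICC" and adds "we will include a covariate for the classification of risk of treatment failure (minimal or elevated) and intervention received". It does not repeat the protocol's reason for including arm.

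Neither document says when visit frequency, OAT/MOUD, SSP use or substance use are measured for this model. Neither HIV suppression section fits arm without cure.

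**The concern.** Whether a randomized intervention had any impact on an outcome is a question about its total effect, by whatever route. A model that holds fixed the consequences of the intervention answers a narrower question: whether support acts on HIV suppression other than through those consequences. If engagement that is not measured drives both cure and suppression, the coefficient is biased even for that narrower question, because comparing arms within cure groups breaks the balance that randomization gave.

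What is at stake is a secondary statement. A coefficient near the null from this model could be reported as no impact of support on HIV suppression, when all it shows is no impact beyond cure and the other adjusted variables.

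**Working it through.** **1. Which covariates lie downstream of arm, on the documents' own account**

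- *Cure.* In the elevated-risk stratum, Protocol 15.3.1 expects that "PWID receiving the high intensity intervention will have significantly higher SVR than those receiving either the medium or the low intensity interventions". Protocol 15.3.2.4 expects that "Among HIV/HCV co-infected PWID, HIV viral suppression will be higher after achievement of HCV cure". Together these make cure a mediator between arm and HIV suppression.
- *MOUD.* SAP 3a analyses MOUD initiation and retention by arm; SAP 2d adjusts for MOUD. It is a mediator unless only a baseline value is used.
- *ICC visit frequency.* Protocol 12.2.6 gives Arm 3 one to seven extra contacts a week, against dispensing every 28 days in Arms 1 and 2. These contacts may take place in the field, and no measurement time is given. Visit frequency may or may not be a mediator.
- *SSP use, substance use, needle sharing.* These could be baseline or follow-up values; the plan does not say.

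**2. Design inputs**

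No figure is stated for HIV suppression, so there is none to reproduce. The SVR inputs used below do reproduce: with 85% SVR in the comparator and 1,500 in the elevated-risk stratum, the detectable RR is 1.075 for high versus low (Table 15.4.1: 1.08) and 1.062 for high versus medium (table: 1.06).

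**3. Effect through cure alone, by hand**

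Take SVR of 85% in the low arm and 0.85 × 1.08 = 91.8% in the high arm. Assume suppression of 50% in uncured participants and a cure odds ratio of 2 or 3 for suppression, which gives 66.7% or 75% in cured participants.

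- Cure OR 2. Low: 0.85 × 0.6667 + 0.15 × 0.50 = 0.6417, odds 1.791. High: 0.918 × 0.6667 + 0.082 × 0.50 = 0.6530, odds 1.882. Total OR = 1.882 / 1.791 = 1.05.
- Cure OR 3. Low: 0.85 × 0.75 + 0.15 × 0.50 = 0.7125, odds 2.478. High: 0.918 × 0.75 + 0.082 × 0.50 = 0.7295, odds 2.697. Total OR = 2.697 / 2.478 = 1.09.

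Simulation with both strata and the 3:2:1 and 1:2:3 allocations gave 1.06 and 1.10, in line with this. Adding cure to the model takes either value to about 1.0.

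**4. Adding a path through visit frequency**

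Further assumptions: cure OR 2; no direct effect of arm; medium-arm SVR 87%; visits measured after entry and raised by 1 SD in the high arm and 0.3 SD in the medium arm; one viral load per person; 1,000 runs per row. Entries are the high versus low OR and power at two-sided 0.05.

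| Log-OR per SD of visits | Co-infected N | Arm + stratum | + cure | + cure + visits |
|---|---|---|---|---|
| 0.5 | 300 | 1.68, 36% | 1.62, 30% | 0.99, 5% |
| 0.5 | 600 | 1.69, 61% | 1.62, 53% | 1.01, 6% |
| 0.5 | 900 | 1.69, 79% | 1.62, 71% | 1.00, 6% |
| 0.3 | 300 | 1.42, 18% | 1.36, 14% | 1.00, 5% |
| 0.3 | 600 | 1.41, 32% | 1.35, 25% | 1.00, 6% |
| 0.3 | 900 | 1.42, 46% | 1.36, 36% | 1.01, 6% |

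Conditioning on cure alone costs 4 to 10 points of power here. A second simulation (600 co-infected, total conditional log-OR 0.8, a latent engagement factor) lost 3 to 5 points from cure alone: 82.7% to 77.6%, 85.2% to 81.2% and 89.6% to 86.9%, according to how much of the effect ran through visits. In both simulations the large loss comes from post-entry visits. In the second, power with cure and visits in the model was 8.8% when visits carried the whole effect, and still 67.8% when they carried none of it.

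**5. Is the coefficient at least a valid direct effect?**

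With a true direct log-OR of 0.3 added to the 0.5 setting, the total OR of 2.25 becomes 1.35 = exp(0.3), so the direct part is recovered. With no direct effect, no visit path and an unmeasured cause shared by cure and suppression, the total OR is 1.06 and the conditioned OR is 0.95. The true direct OR is 1.00, so the coefficient is then biased even as a direct effect.

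**The case against.** The strongest reply is that the total effect is already planned. SAP 3e announces an inverse-probability-of-treatment-weighted average treatment effect for the primary and secondary outcomes, and SAP section 2 lists HIV suppression among the latter. A reader might infer that no analysis anywhere estimates the effect of arm on HIV suppression; a literal reading of 3e contradicts that. But 3e is exploratory, its detailed text concerns SVR and treatment completion, and Protocol 15.7.2.3 limits the same analysis to treatment completion. It may supply the answer; it does not clearly do so.

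Second, SAP 2d drops the sentence giving the arm term its purpose. Read alone, it uses arm as an adjuster in the cure comparison, which is reasonable because arm may affect both cure and suppression. This stands. The problem is the interpretation that Protocol 15.7.2.2 attaches to the coefficient and that the SAP does not withdraw.

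Third, a reader might infer that a real benefit would usually be missed because clinic visits differ by arm by design. The documents do not support this. Directly observed doses may be given in the field, Arms 1 and 2 may receive medication at home, support lasts only 12 to 24 weeks while viral loads accrue for longer, and visit frequency may be a baseline value.

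Fourth, the word received might be taken to mean an as-treated arm variable. Both documents use the same word for arm in the primary analysis, which is explicitly intention to treat, so little can be built on it.

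Finally, the stated objective and hypothesis for this endpoint concern cure. The question about support is an addition, and the primary analysis is untouched.

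**Conclusion.** The point holds as a mismatch between a stated question and the model said to answer it. The arm coefficient in the cured versus not-cured GEE is at best a direct effect of support, and is biased even for that if unmeasured engagement drives both cure and suppression. It should not be reported as the impact of support intensity.

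That direction follows from the trial's own hypotheses. The size does not, because the documents give no co-infected count, suppression rate or effect size. If cure is the only mediator, the distortion is small: a total OR of about 1.06 to 1.10 becomes about 1.0, an effect that 300 to 900 co-infected participants could scarcely detect in any model (power 5% to 6% at cure OR 2). It is large, about 1.4 to 1.7 becoming 1.0, only if visit frequency is measured after entry, is shifted by arm (by 1 SD in these calculations) and itself affects suppression. The simulations use one viral load per person rather than repeated measures, so their power figures are illustrative.

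**What to change.** - Keep the cure model with arm as an adjuster, and state that its arm coefficient is not interpreted as the impact of support.
- For the support question, specify a separate GEE on viral loads taken after randomization, by randomized arm. Include risk stratum (or inverse-probability-of-treatment weights), site and baseline covariates only. Leave out SVR status and post-entry visit frequency, MOUD, SSP use, substance use and needle sharing. Naming HIV suppression explicitly in SAP 3e, with this covariate rule, would be enough.
- State when visit frequency, MOUD, SSP use and substance use are measured for the cure model.
- Bring Protocol 15.7.2.3 and SAP 3e into agreement on which secondary outcomes the average treatment effect covers.

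The cost is some SAP wording and one model on data already being collected. The downside is one more secondary or exploratory result to report.
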